Title: Objective assessment of fatigue or dyspnoea as the mechanism of exercise limitation in heart failure: *Implications for individualised therapy*

1. Introduction

This Statistical Analysis Plan (SAP) predefines statistical analysis, population, variables, and analysis methods of this trial. It is based on the study protocol (ClinicalTrials.gov ID:NCT04332536). The trial has been designed to demonstrate 1) whether a novel exercise test can identify the primary mechanism of exercise limitation in patients with CHF and 2) whether a specific intervention targeting dyspnoea influences exercise tolerance in CHF patients.

2. Rationale

Chronic heart failure (CHF) is a complex multifaceted disease that has a rising prevalence and poor prognosis, imposing an ever-growing demand on limited health care resources: annual CHF costs are ~2 % of the total NHS budget.[1] Optimal contemporary CHF therapy has reduced hospitalisations and extended the life-span of CHF patients, but these treatments are less effective at alleviating symptoms. Thus, there is a large and growing CHF patient population living with persistent and debilitating symptoms.

The primary symptom and a defining characteristic of CHF is exercise intolerance, and it is by the degree of exercise intolerance that CHF severity is clinically defined.[2,3] Impaired exercise tolerance limits the ability to undertake activities of daily living, reduces health-related quality of life, and perpetuates a cycle of inactivity and

deconditioning that further accelerates the decline in functional capacity and disease progression.

The gold-standard measure of exercise tolerance is $\dot{V}O_{2\text{peak}}$ measured from a treadmill or cycle ergometer based cardiopulmonary exercise (CPX) test. $\dot{V}O_{2\text{peak}}$ is the strongest predictor of survival.[4] and interventions that increase $\dot{V}O_{2\text{peak}}$ convey protection against adverse events (i.e. hospitalisations and death).[5] The clinical usefulness of $\dot{V}O_{2\text{peak}}$, and other CPX test parameters (e.g. $\dot{V}E$ / $\dot{V}CO_2$) particularly in relation to prognosis, is established.[4] However, the *mechanism* limiting $\dot{V}O_{2\text{peak}}$ is not identified by current CPX tests. At the point of exercise limitation patients report intolerable fatigue (i.e. muscle limited) or dyspnoea (i.e. symptom limited by breathlessness). Objectively identifying the mechanism of exercise limitation with a CPX test could be an essential first step to target treatments and personalise therapy to ameliorate the exercise limitation across a heterogeneous population of CHF patients.

We developed an innovative CPX technique that distinguishes between fatigue and dyspnoea as the operant mechanism that determines $\dot{V}O_{2\text{peak}}$. We have successfully used this CPX-test in COPD patients.[6,7,8]

This project will use our CPX technique in CHF to provide a step-change in the information provided by traditional CPX tests and understand how fatigue or dyspnoea limits $\dot{V}O_{2\text{peak}}$ in this heterogeneous population (*Objective 1*). An opioid intervention will then be used to demonstrate that our novel CPX technique can: (1) identify the mechanism of exercise limitation; (2) be used to target mechanism-specific therapies

to the aetiology of the exercise limitation. Specifically, our hypothesis is that symptom-alleviation with opioid use will increase exercise tolerance in symptom-limited (breathlessness), but not muscle-limited CHF patients (*Objective 2*).

Limitations to $\dot{V}O_{2\text{peak}}$ in health: $\dot{V}O_{2\text{peak}}$ measured during dynamic whole-body exercise (e.g. walking or cycling) quantifies the capacity of the O₂ cascade to deliver *and* utilise O₂. The effectiveness of the O₂ cascade determines the extent to which oxidative phosphorylation can meet the demands for ATP turnover, minimising the requirement for substrate-level phosphorylation and associated accumulation of fatigue-related metabolites. This is particularly important as these fatigue-related metabolites are directly associated with muscle fatigue and indirectly increase ventilation, thus contribute to dyspnoea. Therefore, task failure at $\dot{V}O_{2\text{peak}}$ could be due to (a) fatigue-induced reductions in the capacity of the neuromuscular system to voluntarily generate power such that the required power for the task can no longer be produced (i.e. $\dot{V}O_{2\text{peak}}$ muscle-limited), or (b) overwhelming symptoms of dyspnoea that result in exercise cessation prior to muscular limits for power production being attained. The latter situation implies a reserve in the capacity of the exercising muscle to generate power above that required by the task (i.e. $\dot{V}O_{2\text{peak}}$ symptom-limited). These opposing mechanisms could be considered as ‘unable’ to continue the exercise (muscle-limited) vs. ‘unwilling’ to continue due to overwhelming dyspnoea (symptom-limited).[9] Identifying the aetiology of the exercise limitation offers the intriguing potential to personalise the approach to interventions designed to ameliorate exercise intolerance and thereby symptoms.

The novel exercise test: To investigate this, we have developed an innovative CPX test to distinguish between these opposing mechanisms of task failure at $\dot{V}O_{2\text{peak}}$. This CPX test uses a commercially available cycle ergometer that has two key features; (1) strain gauges in the crank that directly measure the force produced by the leg muscles during cycling every 2° of pedal rotation, allowing calculation of instantaneous power production; and (2) the ability to switch instantaneously from standard hyperbolic, cadence-independent cycling, to isokinetic cycling (experimentally-controlled, constant cadence). Since muscle torque is velocity dependent, isokinetic (cadence-controlled) measurements are essential to appropriately measure maximal voluntary neuromuscular power producing capacity in both the fresh and fatigued state.[10]

Using our CPX test we can therefore measure the power-producing capacity of the leg muscles at any point during an exercise task from a brief (~ 5 s) maximal isokinetic effort. By comparing this maximal voluntary isokinetic power (MVIP) with the instantaneous demands of the exercise task (power set on the cycle ergometer), we can delineate between muscle and symptom limitations. In a single test we make three power measurements that might be clinically important: 1. Fresh MVIP at baseline (MVIP_{FRESH}); 2. the standard cycle ergometer measure of power at $\dot{V}O_{2\text{peak}}$ (P- $\dot{V}O_{2\text{peak}}$) 3. MVIP in the fatigued state, instantaneously at the point of $\dot{V}O_{2\text{peak}}$ at task failure (MVIP_{FATIGUE}; Figure 1).

[figure not shown]

Figure 1: Healthy participant responses to our innovative ramp-incremental CPX test in which fresh maximal voluntary isokinetic power (□ **MVIP_{FRESH}**) decreases as the ramp-incremental test progresses to the extent that at $\dot{V}O_{2\text{peak}}$ (○) fatigued maximal voluntary isokinetic power (□ **MVIP_{FATIGUE}**) is not different from ramp-incremental power (**P- $\dot{V}O_{2\text{peak}}$**); i.e. there is no power reserve at $\dot{V}O_{2\text{peak}}$ ^[7]

These power measurements allow us to assess skeletal muscle power generating capacity (MVIP_{FRESH}), and the mechanism of task failure at $\dot{V}O_{2\text{peak}}$, delineating fatigue (muscle-limited) from dyspnoea (symptom-limited) through comparison of P- $\dot{V}O_{2\text{peak}}$ and MVIP_{FATIGUE} – the so-called ‘power reserve’ (Figure 1) – allowing us to provide the following important differentiation at the end of the test:

- No power reserve: The absence of a meaningful difference between P- $\dot{V}O_{2\text{peak}}$ and MVIP_{FATIGUE} – the capacity of the neuromuscular system to voluntarily generate the required task power has been reached at $\dot{V}O_{2\text{peak}}$, and fatigue is preventing continuation of the ramp-incremental task, i.e. exercise is muscle-limited.
- Power reserve: MVIP_{FATIGUE} exceeds P- $\dot{V}O_{2\text{peak}}$ – there is capacity within the neuromuscular system to voluntarily generate more power than is required by the task and therefore the exercise is symptom-limited.

In young (~30 yr; n = 20) and older (~65 yr; n = 12) healthy participants we have demonstrated that standard ramp-incremental exercise is commonly terminated at $\dot{V}O_{2\text{peak}}$ with no meaningful power reserve,[6,7,8] (MVIP_{FATIGUE} ~30 % greater than P- $\dot{V}O_{2\text{peak}}$ at task failure; 274±73 vs. 212±84 Watts in healthy older participants[8]), consistent with fatigue determining task failure at $\dot{V}O_{2\text{peak}}$. Thus, in health during standard ramp-incremental exercise, physiologic and sensory responses are closely

associated and increasing effort, even for a very brief time (~ 5 s) is unable to increase $\dot{V}O_{2\text{peak}}$ or instantaneous power. Overcoming this muscle limitation thus requires interventions such as exercise training that increase physiologic capacity and fatigue resistance by increasing muscle O₂ delivery, capillarity and oxidative capacity.

Influence of chronic disease on limitations to $\dot{V}O_{2\text{peak}}$: While the triggering cardiac event leading to CHF impairs cardiac function, the absence of a relationship between $\dot{V}O_{2\text{peak}}$ and heart function,[11] highlights the predominance of systemic consequences of CHF in contributing to the reduction in $\dot{V}O_{2\text{peak}}$. Whilst limits to $\dot{V}O_{2\text{peak}}$ were considered to be primarily the consequence of reduced skeletal muscle O₂ delivery due to cardiac dysfunction it is now clear that there are considerable peripheral influences. Peripheral haemodynamics are adversely affected by persistent sympathetic activation and humorally-mediated vasoconstriction impair skeletal muscle O₂ delivery during exercise. However, skeletal muscle maladaptations also contribute to the reduction in $\dot{V}O_{2\text{peak}}$ by reducing O₂ utilisation. For example, in CHF there is loss of type I fibres, reductions in mitochondrial volume, density, function and muscle capillarity that reduce muscle oxidative capacity. These pathophysiological changes throughout the O₂ cascade result in a more fatigable skeletal muscle phenotype (greater muscle limitation).[12] In CHF there is also decreased ventilatory efficiency (high $\dot{V}E/\dot{V}CO_2$), manifest as a consequence of altered ventilatory control (low PaCO₂) and high ventilation-perfusion mismatch (high V_D/V_T), that increases the ventilatory requirements of exercise, work of breathing and dyspnoea (greater symptom limitation).[13]

Thus, exercise limitation in CHF is a complex interplay between increased fatigue and increased dyspnoea. Which operant mechanism predominates is currently unknown, cannot be identified by traditional CPX-tests, and might be different between patients in whom the severity of exercise limitation is the same. Using our innovative CPX approach can now make the distinction between intolerable fatigue (i.e. muscle limited) or dyspnoea (i.e. symptom limited by breathlessness).

CHF pilot data: In contrast to the response seen in health, in CHF patients (n=16), we have shown that ramp-incremental exercise is terminated at $\dot{V}O_{2\text{peak}}$ with a large power reserve. MVIP_{FATIGUE} was, on average, $101\pm122\%$ greater than P- $\dot{V}O_{2\text{peak}}$ (213 ± 132 vs. 109 ± 44 Watts, RM-ANOVA with Dunnett *post-hoc*,[7] $p = 0.002$, 95% CI_{Difference} 38, 171 Watts; Figure 2). This power reserve suggests the physiologic and sensory responses have become dissociated and $\dot{V}O_{2\text{peak}}$ is symptom-limited in CHF. This is similar to our observation in COPD patients where MVIP_{FATIGUE} was $\sim 160\%$ greater than P- $\dot{V}O_{2\text{peak}}$ at task failure.[8]

[figure not shown]

Figure 2: Representative examples of CHF patient responses to our innovative ramp-incremental CPX test. Fresh maximal voluntary isokinetic power (□ MVIP_{FRESH}) decreases as the test progresses. **A.** Fatigued maximal voluntary isokinetic power (□ MVIP_{FATIGUE}) at $\dot{V}O_{2\text{peak}}$ (○) is greater than the ramp-incremental power (P- $\dot{V}O_{2\text{peak}}$): the power reserve suggests exercise in this patient is symptom-limited. **B.** MVIP_{FATIGUE} was not meaningfully different from P- $\dot{V}O_{2\text{peak}}$: the absence of a power reserve suggests exercise in this patient is muscle-limited.

In our CHF patients, we also observed two key phenotypes:

1. CHF patients ($n = 6$) without a power reserve ($MVIP_{FATIGUE} 22 \pm 12\%$ greater than $P\dot{V}O_{2\text{peak}}$ at task failure; 141 ± 66 vs. 115 ± 47 Watts $p = 0.547$, $CI_{\text{Difference}} -44, 97$ Watts), suggesting they reached their physiological limits and are muscle-limited (Figure 2B).
2. CHF patients ($n = 10$) in whom the power reserve was substantial ($MVIP_{FATIGUE} 149 \pm 134\%$ greater than $P\dot{V}O_{2\text{peak}}$ at task failure; 256 ± 145 vs. 105 ± 44 Watts $p = 0.002$, $CI_{\text{Difference}} 55, 246$ Watts), suggesting $\dot{V}O_{2\text{peak}}$ was symptom-limited (Figure 2A).

Importantly, this objective CPX-test measure of the power reserve that identifies whether fatigue or dyspnoea is the primary mechanism of exercise limitation is unique. The presence of a relevant power reserve cannot be identified from traditional subjective ratings of perceived exertion (RPE). The mechanisms that determine effort, e.g. the effort required to turn the legs during cycling, interact with dyspnoea, meaning that the RPE of leg effort is heightened with dyspnoea, independent of objective measures of leg fatigue, and *vice versa*. Therefore, objectively identifying the primary limitation to exercise is critical and can only be identified using our technique.

Effect of opioids on exercise tolerance: In COPD patients during maximal constant-load exercise, immediate-release oral morphine decreased breathing frequency, ventilation and Borg ratings of dyspnoea. This was associated with a clinically meaningful ($+ 2.5 \pm 0.9$ min) increase in time to task failure,[14] consistent with our suggestion above that dyspnoea can limit exercise tolerance, and when dyspnoea is attenuated in patients who are symptom-limited (and not fatigue-limited), the skeletal muscle is capable of performing more work. While these data are consistent with other studies showing reductions in dyspnoea and increases in exercise tolerance with

systemic opioids in COPD,[15,16] this study also identified 'responders' and 'non-responders'.[14] Whilst our innovative CPX test revealed that mean MVIP_{FATIGUE} was on average ~160% greater than P- $\dot{V}O_{2\text{peak}}$ in COPD and that some patients were therefore symptom-limited with a large power reserve, there appeared to be a subgroup of muscle-limited patients with no meaningful power reserve,[8] in whom we hypothesise opioid treatment would have no effect, due to the absence of a power reserve. This heterogeneous response mirrors that seen in our pilot CHF data.

In CHF opioids reduced symptoms of dyspnoea,[17] increase exercise time (~12 % increase in tolerable duration) and $\dot{V}O_{2\text{peak}}$ [18] ($+1.6 \text{ ml} \cdot \text{min}^{-1} \cdot \text{kg}^{-1}$; MCID = $1 \text{ ml} \cdot \text{min}^{-1} \cdot \text{kg}^{-1}$ [19]). However, similar to the variable response seen in COPD, the effect is inconsistent across CHF patients, possibly due to the heterogeneity in the mechanism of exercise limitation that has previously not been discernible. We believe that we can now divide CHF patients into two groups using our novel CPX approach (Figure 2).

Compared with alternative interventions (e.g. device, medical, rehabilitation) that affect *both* fatigue and dyspnoea in combination, opioid treatment specifically targets dyspnoea. Thus, objective 2 aims to demonstrate that our CPX-test can for the first time identify likely 'responders' (symptom-limited) and 'non-responders' (muscle-limited) to this mechanism-specific, symptom-alleviating opioid intervention (*Objective 2*) whilst also confirming our hypothesis of two phenotypes within the exercise intolerance CHF population. This will also provide the first evidence that the mechanisms limiting exercise tolerance in CHF are directly modifiable and can be selectively targeted by personalised interventions to maximise therapeutic efficacy.

3 Study design and randomisation

Design: This study is a randomised, double-blinded, crossover, multi-group trial conducted at one centre in the UK (Leeds Teaching Hospitals NHS Trust).

Participants: The study will recruit a total of 100 subjects of whom 75 will have HF with reduced ejection fraction (HFrEF) and 25 will be control subjects.

Inclusion criteria: Patients with CHF due to left ventricular systolic dysfunction (NYHA II or III, and left ventricular ejection fraction < 50%), optimally tolerated stable medical therapy, able and willing to provide written informed consent and perform CPX-tests.

Exclusion criteria: CHF without symptoms or class IV symptoms, any contraindications to exercise or severe neuromuscular disability limiting exercise, significant COPD (FEV1 < 50%) or other significant respiratory disease contributing to symptoms, or renal disease (eGFR < 20).

Study activities and exercise protocols: After baseline assessments (resting echocardiography, demographics, resting ECG, medical history, medication review) are complete, each participant will perform one maximum effort ramp-incremental cardiopulmonary exercise test on an electromagnetically braked cycle ergometer which allows for the measurement of maximal voluntary isokinetic power (at baseline and immediately end ramp-incremental exercise MVIP_{FRESH}, MVIP_{Fatigue}) along with the traditional measure of ramp-incremental power at peak exercise.

At three subsequent visits each approximately one week apart, participants will perform an exercise test at a constant power of around 70-80% ramp-incremental

power at peak exercise until they cannot continue. The exercise power of these tests has been chosen aiming for a duration of the test to be between approximately 4 and 8 minutes.

Of these three tests, tests one and two will be maximum effort constant power exercise and will be continued until the point of exercise intolerance, and will be performed following a single dose of either dihydrocodeine or placebo (randomised).

The third test will be performed at the same constant power, following the same condition during which the participant achieved the longest exercise time, but will be terminated at the time of the shorter test (the iso-time test). The investigators will be blinded to whether this was with dihydrocodeine or placebo ensuring that the rigours of double-blinding are maintained. This third test is important because, as is increasingly appreciated, the important variables at the end of an exercise test ($\dot{V}O_{2\text{peak}}$, $\text{MVIP}_{\text{FATIGUE}}$, dyspnoea) may be the same at the point of exercise intolerance with dihydrocodeine and placebo, but the rate at which these end-points are achieved may be different.

Intervention: Prior to the first two constant power tests, subjects will be asked to take a sweetened oral solution containing 0.5mg/kg dihydrocodeine up to a maximum of 60mg, or placebo solution with matching colour/taste, a minimum of 30 minutes prior to the test. Prior to the third constant power test, subjects will be asked to take the intervention that was associated with the longest exercise time during the first two tests.

Primary outcome measures: During each test we will measure power, pulmonary gas exchange ($\dot{V}O_2$, $\dot{V}CO_2$, $\dot{V}E$, RER, tidal volume, breathing frequency), haemodynamic variables such as blood pressure and heart rate ECG, oxygen saturation (Ultima Cardio2, Medical Graphics) throughout. As described above, the use of an electromagnetically braked cycle ergometer, will provide the opportunity to measure $MVIP_{FRESH}$, $MVIP_{Fatigue}$ from power measurements made directly at the crank of the cycle ergometer (Figure 3).

[figure not shown]

Figure 3: Schematic of the innovative ramp-incremental CPX protocol (objective 1). Ramp-incremental exercise will be replaced by constant-work rate exercise to address objective 2. All other measurements and procedures will be identical.

Borg scale ratings of perceived exertion (leg fatigue and breathlessness) will be recorded every 2 minutes during exercise, and at $\dot{V}O_{2peak}$.

Blinding: Subjects and observers will be blinded to allocation for all three tests. Leeds Pharmacy will be provided with the exercise duration for the first two constant power tests and allocate either dihydrocodeine or placebo at the third test based on which gave the longest exercise duration in the first two constant power tests.

4 Aims and objectives

Overarching objective: To determine whether a novel CPX-test can identify the primary mechanism of exercise limitation in CHF, and be used to target mechanism-specific interventions personalised to the driving pathophysiology in individuals.

Objective 1: Characterise fatigue vs. dyspnoea limitations to $\dot{V}O_{2\text{peak}}$ in CHF using novel power measurements made during the CPX.

Objective 2: Investigate the efficacy of symptom-alleviating opioid treatment to increase exercise tolerance in CHF.

5. Sample size calculation

5.1 Objective 1: Phenotyping the mechanism of exercise limitation

To identify if the power reserve is different between CHF patients vs. controls (two-tailed independent t-test), assuming a standard deviation of 40% (based on our CHF pilot data) we require 60 CHF and 20 control patients to have 90% power to detect an absolute power reserve difference of 30% at $p < 0.05$. The 3:1 ratio allows adequate power for our secondary analysis comparing the 3 different severities of CHF, where 20 in each group gives us 80% power to detect a linear trend over the 3 categories of increasing severity, with a mean power reserve difference of 20 percentage points in absolute terms between each group, e.g. 20 % vs 40 % vs 60 % power reserve with increasing severity. In anticipation that we may need to log-transform our primary outcomes due to non-normally distributed data, our power calculation is conservative. To allow for any drop-out, and any unsuccessful test, we propose recruiting an additional 25% (*Objective 1*). Hence, we will invite 75 people with CHF and 25 controls to participate.

5.2: Objective 2: Efficacy of intervention

Based on exercise on a conservative effect size (f) of 0.300,[18] and a conservative correlation between repeated measures of 0.5,[14] 17 patients in each group gives us 90% power at $p < 0.05$. Thus, we will be powered to detect a smaller increase in

exercise duration than that found in COPD.[14] We will recruit 20 patients to allow for any drop-out (*Objective 2*).

6. Planned analyses

6.1 Objective 1

6.1.1 Endpoints for objective 1

In *Objective 1* we will use the power reserve to describe the frequency of muscle-limited vs. dyspnoea (symptom)-limited CHF patients and controls and describe these phenotypes by clinical severity and cardiopulmonary variables.

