8.2.4 Objective 1 analyses

These will use the power reserve to describe the frequency of fatigue vs. dyspnoea limitations to $\dot{V}O_{2\text{peak}}$ in CHF compared with controls and also compare the magnitude of the power reserve along with relevant clinical characteristics of participants with either limiting factor using appropriate tests depending upon the nature of the data.

We will then proceed to explore the relationships between the relevant clinical characteristics, the power reserve, other power variables (e.g. MVIP_{FRESH}, P- $\dot{V}O_{2\text{peak}}$, MVIP_{FATIGUE}) and ventilatory and pulmonary gas exchange variables (e.g. $\dot{V}O_2$, $\dot{V}CO_2$, $\dot{V}E$, RER, tidal volume, breathing frequency).

All model assumptions will be checked to ensure the residuals are normal, and that the residuals are independent with no evidence of homoscedasticity.

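### Section 5.1 claims 90% power for 60 CHF patients and 20 controls, but its own inputs give about 82%, and its 40% SD does not match the pilot it cites (122%)

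*SAP*

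**What the plan says.** Section 5.1 plans a two-tailed independent t-test of power reserve, CHF against controls, at p < 0.05 for an absolute difference of 30%: "assuming a standard deviation of 40% (based on our CHF pilot data) we require 60 CHF and 20 control patients to have 90% power". It then inflates the numbers: "To allow for any drop-out, and any unsuccessful test, we propose recruiting an additional 25"%, giving 75 CHF patients and 25 controls.

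The 3:1 ratio is justified by a secondary analysis of three CHF severity groups, "where 20 in each group gives us 80% power to detect a linear trend over the 3 categories of increasing severity", with steps of 20 points. The section adds that, because a log-transform may be needed "due to non-normally distributed data, our power calculation is conservative".

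The pilot is described in section 2. In 16 CHF patients, fatigued isokinetic power "was, on average, $101\pm122\%$ greater than" ramp power at peak. Six patients without a reserve had 22 ± 12%. The other ten are those "in whom the power reserve was substantial ($MVIP_{FATIGUE} 149 \pm 134\%$ greater than" ramp power. For healthy older participants section 2 gives "274±73 vs. 212±84 Watts in healthy older participants", an excess of about 30%.

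Section 8.2.4 leaves the Objective 1 test open, "using appropriate tests depending upon the nature of the data".

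**The concern.** Section 5.1 gives every input needed to recompute its power, and the result is not 90%. The SD is attributed to a pilot that the same document reports with an SD about three times as large.

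The 90% figure is the stated justification for the Objective 1 sample size. If it is wrong, a null CHF-control comparison or a null severity trend will be read as stronger evidence than it is. If the SD cannot be traced, a reader cannot tell what difference the study is able to detect.

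**Working it through.** **Inputs (section 5.1).** Difference 30 points; SD 40 in both groups; 60 CHF and 20 controls; two-sided 5%. Section 8.2.1 also sets two-sided tests at 5%.

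**1. Power from the stated inputs**

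- SE = 40 × √(1/60 + 1/20) = 10.33
- Noncentrality = 30 / 10.33 = 2.905, with df = 78
- Power = 81.8% (noncentral t), or 82.8% (normal approximation)

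The stated 90% is not reproduced. The type II error is about 18%, not 10%.

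**2. What would give about 90%**

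| Change | Power (t) | Agrees with section 5.1? |
|---|---|---|
| 75 and 25 evaluable | 89.5% (normal 90.1%) | No: these are 60 and 20 plus the loss allowance |
| One-sided 5% | 89.1% | No: two-tailed |
| 40 and 40 | 91.2% | No: 3:1 |
| 60 and 20, difference 33.9 | 90% | No: 30 |
| 60 and 20, SD 35.4 | 90% | No: 40 |

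At SD 40 and 30 points, power falls from 89.5% with no loss to 86.8% at 68 and 23 evaluable (about 9% lost), and to 81.8% when the whole allowance is used.

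**3. The pilot SD**

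Recombining the two pilot subgroups from section 2:

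- Mean = (6×22 + 10×149)/16 = 101.4
- SD = √{[5×12² + 9×134² + 6×(22 − 101.4)² + 10×(149 − 101.4)²]/15} = 121.9

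This matches the reported 101 ± 122%. The ± values are therefore SDs, and the pilot SD is 122%. The SDs reported for the CHF power reserve are 12, 122 and 134%; none is 40%.

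**4. Power at 60 and 20 with a CHF SD of 122**

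The SAP gives no control SD for the power reserve, so a range is assumed. Figures for the two-group comparison are from simulation of normal data (200,000 replicates). The 71-point gap is 101 − 30, from the CHF pilot and the healthy older participants in section 2 (274/212 = 1.29).

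| Assumed control SD | 30 points: unequal-variance / pooled | 71 points: unequal-variance / pooled |
|---|---|---|
| 20 | 44% / 8% | 99% / 83% |
| 40 | 37% / 9% | 97% / 80% |
| 60 | 30% / 11% | 92% / 75% |
| 122 | 15% / 16% | 59% / 61% |

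The difference detectable with 90% power by the unequal-variance test is about 54, 59 and 68 points for control SDs of 20, 40 and 60.

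**5. Severity trend (CHF only, so no control SD is needed)**

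There are 20 patients per group and an end-to-end difference of 40 points; SE = SD × √(2/20), df = 57.

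- SD 40: SE = 12.65, noncentrality 3.16, power 87%
- SD 122: SE = 38.58, noncentrality 1.04, power 17%

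On its own SD the trend statement of 80% is met with room to spare. At the pilot SD it is not.

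**The case against.** The strongest defence of the 90% is that the trial recruits 75 and 25, and those numbers do give about 90%. That is true only if nobody drops out and no test fails, and section 5.1 introduces the larger numbers precisely because it expects some loss.

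On the SD, section 5.1 does not define the denominator of its percentage, and its example of 20, 40 and 60% lies well below the pilot mean of 101%. The 40% could come from another scale or subset. This cannot be excluded, but the SAP does not say so, section 2 expresses the reserve relative to ramp power, and the 30-point target is in absolute terms. A log scale does not obviously explain it either: if the ratio of fatigued to ramp power were lognormal with mean 2.01 and SD 1.22, its log SD would be √ln(1 + (1.22/2.01)²) ≈ 0.56.

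Three further points stand in part:

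- The power figures at SD 122 assume normal data and a control SD. A pilot of 16 patients in two dissimilar clusters is plainly not normal, so these figures show sensitivity and are not exact.
- The trend claim is not wrong on its own inputs.
- The Objective 1 analysis is largely descriptive and the sample size is already set, so the correction bears on interpretation and not on any estimate. Even so, section 5.1 justifies the size by a powered test, and sections 6.1.3 and 8.2.4 do compare the groups.

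**Conclusion.** The point holds; the power statement is wrong as written. On section 5.1's own inputs, power at 60 and 20 is 82%, a shortfall of about 8 percentage points that needs no outside assumption. The 40% SD matches no CHF power-reserve SD reported in section 2, where the overall figure is 122%.

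How far true power falls short depends on the control SD and on the true difference. If 30 points is kept as the target and the pilot SD is right, power is far below 90% under every control SD tried. At about 71 points it may be adequate: 92-99% with an unequal-variance test and control SD 20 to 60, but 75-83% with a pooled test and about 60% if controls vary as much as patients. That gap also assumes the trial's controls resemble the healthy older participants in section 2.

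The claim that the calculation is conservative is a lesser matter. No log-scale SD or effect is given, so it cannot be checked.

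**What to change.** In section 5.1:

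1. Replace 90% with 82% for 60 and 20, and add that about 90% applies only if all 75 and 25 are evaluable. A difference of 34 points at 90% is arithmetically equivalent, but the 30-point target should not be moved merely to keep the 90%.
2. State where the 40% SD comes from and on what scale, or replace it with the pilot's 122%. Give a control SD.
3. On that basis, restate the power or detectable difference for CHF against controls, and for the severity trend.
4. Support the remark about being conservative with log-scale inputs, or delete it.

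Optionally, name the unequal-variance (Welch) t-test for CHF against controls in section 8.2.4. With a larger spread in the larger group at 3:1, a pooled test loses much of the power.

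The cost is SAP wording only. The stated power becomes less favourable; recruitment, data and endpoints are unchanged. The correction does not itself call for more patients, though whether 75 and 25 suffice depends on the difference and the control SD that are then stated.
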